25.2 Definitions

25.2.1 Adverse Event (AE)

An AE is any untoward medical occurrence in a clinical study subject administered a medicinal (investigational or non-investigational) product. An adverse event does not necessarily have a causal relationship with the treatment. An adverse event can therefore be any unfavorable and unintended sign (including an abnormal finding), symptom, or disease temporally associated with the use of a medicinal (investigational or non-investigational) product, whether or not related to that medicinal (investigational or non-investigational) product. (Definition per International Conference on Harmonisation [ICH])

This includes any occurrence that is new in onset or aggravated in severity or frequency from the baseline condition, or abnormal results of diagnostic procedures, including laboratory test abnormalities.

Adverse events may include, but are not limited to:

- Subjective or objective symptoms provided by the patient and/or observed by the Investigator or study staff including laboratory abnormalities of clinical significance.
- Any AEs experienced by the patient through the completion of final study procedures.
- AEs not previously observed in the patient that emerge during the protocol-specified AE reporting period, including signs or symptoms associated with cGVHD that were not present before the AE reporting period
- Complications that occur as a result of protocol-mandated interventions (e.g., invasive procedures such as biopsies).

The following are NOT considered AEs:

- **Pre-existing condition:** A pre-existing condition (documented on the medical history CRF) is not considered an AE unless the severity, frequency, or character of the event worsens during the study period.
- **Pre-planned or elective hospitalization:** A hospitalization planned before signing the informed consent form is not considered an SAE, but rather a therapeutic intervention. However, if during the pre-planned hospitalization an event occurs, which prolongs the hospitalization or meets any other SAE criteria, the event will be considered an SAE. Surgeries or interventions that were under consideration, but not performed before enrollment in the study, will not be considered serious if they are performed after enrollment in the study for a condition that has not changed from its baseline level. Elective hospitalizations for social reasons, solely for the administration of chemotherapy, or due to long travel distances are also not SAEs.
- **Diagnostic Testing and Procedures:** Testing and procedures should not to be reported as AEs or SAEs, but rather the cause for the test or procedure should be reported.

For the purposes of this clinical study, AEs include events which are either new or represent detectable exacerbations of pre-existing conditions as measured prior to HCT and prior to administration of ibrutinib.

Adverse Events of Special Interest

Adverse events of special interest are events that Janssen Scientific Affairs, LLC. is actively monitoring as a result of a previously identified signal (even if non-serious). These adverse events are:

Major Hemorrhage

Major hemorrhage is defined as:

- Any treatment-emergent hemorrhagic AE of Grade 3 or higher*
- Any treatment-emergent SAE of bleeding of any grade
- Any treatment-emergent CNS hemorrhage/hematoma of any grade
- **all hemorrhagic AEs requiring a transfusion of red blood cells should be reported as a Grade 3 or higher AEs per NCI-CTCAE*

Any Adverse Event of Special Interest that is to be reported to Janssen Scientific Affairs, LLC should be recorded on a Serious Adverse Event Report Form and be reported to Janssen Scientific Affairs, LLC **within 24 hours of knowledge of the event.**

25.2.2 Serious Adverse Event (SAE)

A serious adverse event based on ICH and EU Guidelines on Pharmacovigilance for Medicinal Products for Human Use is any untoward medical occurrence that at any dose:

- Results in death (i.e., the AE actually causes or leads to death).
- Is life-threatening. Life-threatening is defined as an AE in which the patient was at risk of death at the time of the event. It does not refer to an event which hypothetically might have caused death if it were more severe. If either the Investigator or the Sponsor believes that an AE meets the definition of life-threatening, it will be considered life-threatening.
- Requires in-patient hospitalization >24 hours or prolongation of existing hospitalization.
- Results in persistent or significant disability/incapacity (i.e., the AE results in substantial disruption of the patient's ability to conduct normal life functions).
- Is a congenital anomaly/birth defect.
- Is a suspected transmission of any infectious agent via a medicinal product
- Is an important medical event that may not result in death, be immediately life-threatening or require hospitalization, but may be considered an SAE when, based upon appropriate medical judgment, the event may jeopardize the patient or patient may require intervention to prevent one of the other outcomes listed in this definition. Examples of such events are intensive treatment in an emergency department or at home for allergic bronchospasm, blood dyscrasias, or convulsion that does not result in hospitalization; or development of drug dependency or drug abuse.

Medical and scientific judgment should be exercised in deciding whether expedited reporting is also appropriate in other situations, such as important medical events that may not be immediately life threatening or result in death or hospitalization but may jeopardize the subject or may require intervention to prevent one of the other outcomes listed in the definition above. These should usually be considered serious.

Severity Criteria (Grade 1-5)

Definitions found in the Common Terminology Criteria for Adverse Events version 4.03 (CTCAE v4.03) will be used for grading the severity (intensity) of AEs. The CTCAE v4.0 displays Grades 1 through 5 with unique clinical descriptions of severity for each referenced AE. Should a patient experience any AE not listed in the CTCAE v4.03, the following grading system should be used to assess severity:

- Grade 1 (Mild AE) – experiences which are usually transient, requiring no special treatment, and not interfering with the patient’s daily activities
- Grade 2 (Moderate AE) – experiences which introduce some level of inconvenience or concern to the patient, and which may interfere with daily activities, but are usually ameliorated by simple therapeutic measures
- Grade 3 (Severe AE) – experiences which are unacceptable or intolerable, significantly interrupt the patient’s usual daily activity, and require systemic drug therapy or other treatment
- Grade 4 (Life-threatening or disabling AE) – experiences which cause the patient to be in imminent danger of death
- Grade 5 (Death related to AE) – experiences which result in patient death

Adverse Event Reporting Timeframe

Adverse events will be captured from the time of consent until 30 days post cessation of study drug.

Causality (Attribution)

The Investigator is to assess the causal relation (i.e., whether there is a reasonable possibility that the study drug caused the event) using the following definitions:

- Definite – The AE is clearly related to the study treatment
- Probable – The AE is likely related to the study treatment
- Possible – The AE may be related to the study treatment
- Unlikely - The AE is doubtfully related to the study treatment
- Unrelated - The AE is clearly NOT related to the study treatment

NOTE: DEATH FOR ANY REASON SHOULD BE REPORTED AS A SERIOUS ADVERSE EVENT.

Hospitalization

For reports of hospitalization, it is the sign, symptom or diagnosis which led to the hospitalization that is the serious event for which details must be provided.

Any event requiring hospitalization or prolongation of hospitalization that occurs during the study must be reported as a serious adverse event, except hospitalizations for the following:

- Hospitalizations not intended to treat an acute illness or adverse event (e.g., social reasons such as pending placement in long-term care facility)
- Surgery or procedure planned before entry into the study. [Note: Hospitalizations that were planned before the start of data collection and where the underlying condition for which the hospitalization was planned has not worsened will not be considered serious adverse events. Any adverse event that results in a prolongation of the originally planned hospitalization is to be reported as a new serious adverse event.]

Life-Threatening Conditions

Disease progression should not be recorded as an adverse event or serious adverse event term; instead, signs and symptoms of clinical sequelae resulting from disease progression/lack of efficacy will be reported if they fulfill the serious adverse event definition.

25.3 Individual Case Safety Report (ICSR)

A valid ICSR must contain the four minimum criteria required to meet regulatory reporting requirements:

- an identifiable subject (but not disclosing personal information such as the subject's name, initials or address)
- an identifiable reporter (investigational site)
- a J&J medicinal product
- an adverse event, outcome, or certain special situations

The minimum information required is:

- suspected Janssen medicinal product (doses, indication)
- date of therapy (start and end date, if available)
- batch or lot number, if available
- subject details (subject ID and country)
- gender
- age at AE onset
- reporter ID
- adverse event detail (AE verbatim in English), onset date, relatedness, causality, action taken, outcome, (if available)
- J&J protocol ID

25.4 Product Quality Complaint (PQC)

A product quality complaint is defined as any suspicion of a product defect related to a potential quality issue during manufacturing, packaging, release testing, stability monitoring, dose preparation, storage or distribution of the product, or delivery system. Not all PQCs involve a subject. Lot and batch numbers are of high significance and need to be collected whenever available.

Examples of PQC include but not limited to:

- Functional Problem: e.g., altered delivery rate in a controlled release product

- Physical Defect: e.g. abnormal odor, broken or crushed tablets/capsules
- Potential Dosing Device Malfunction: e.g. autoinjector button not working, needle detaching from syringe
- Suspected Contamination
- Suspected Counterfeit

25.5 Unlisted (unexpected) Adverse Event/Reference Safety Information

An “unexpected” AE is an AE that is not listed in the Investigator's Brochure/package insert or is not listed at the specificity or severity that has been observed. For example, hepatic necrosis would be “unexpected” (by virtue of greater severity) if the Investigator's Brochure referred only to elevated hepatic enzymes or hepatitis. Similarly, cerebral thromboembolism and cerebral vasculitis would be “unexpected” (by virtue of greater specificity) if the Investigator's Brochure/package insert listed only cerebral vascular accidents. "Unexpected" also refers to AEs that are mentioned in the Investigator's Brochure as occurring with a class of drugs or as anticipated from the pharmacological properties of the drug, but are not specifically mentioned as occurring with the study drug under investigation.

<https://www.imbruvicahcp.com/>

https://www.imbruvicahcp.com/docs/librariesprovider2/pdf-downloads/prescribing_information.pdf

25.6 Special Reporting Situation

Safety events of interest for a J&J medicinal product that expedited reporting and/or safety evaluation include, but are not limited to:

- Drug exposure during pregnancy (maternal and paternal)
- Overdose of a J&J medicinal product
- Exposure to a J&J medicinal product from breastfeeding
- Suspected abuse/misuse of a J&J medicinal product
- Inadvertent or accidental exposure to a J&J medicinal product
- Any failure of expected pharmacological action (i.e. lack of effect) of a J&J medicinal product
- Medication error involving a J&J medicinal product (with or without subject/patient exposure to the study drug, e.g., name confusion)
- Suspected transmission of any infectious agent via administration of a medicinal product
- Unexpected therapeutic or clinical benefit from use of a J&J medicinal product

Occurrence of any special reporting situations should be recorded in the eCRF. If any special reporting situation meets the criteria of an adverse event, it should be recorded on the adverse events eCRF. If the adverse event is considered serious, it should be recorded on the adverse events eCRF as serious and should be reported on the Serious Adverse Event Report Form. The SAE Report Form should be sent via email or fax to the Coordinating Center. See the Safety Data Collection and Reporting section for Coordinating Center contact information. Collection of these events will occur from the time the subject signs consent to 30 days after the last dose of study drug.

25.7 Pregnancy

Before study enrollment, subjects must agree to take appropriate measures to avoid pregnancy.

However, should a pregnancy occur in a female study subject, consent to provide follow-up information regarding the outcome of the pregnancy and the health of the infant until 30 days old will be requested.

A female subject must immediately inform the Investigator if she becomes pregnant from the time of consent to 30 days after the last dose of study drug. A male subject must immediately inform the Investigator if his partner becomes pregnant from the time of consent to 3 months after the last dose of study drug. Any female subjects receiving study drug(s) who become pregnant must immediately discontinue study drug. The Investigator should counsel the subject, discussing any risks of continuing the pregnancy and any possible effects on the fetus.

Although pregnancy itself is not regarded as an adverse event, the outcome will need to be documented. Any pregnancy occurring in a subject or subject's partner from the time of consent to 30 days after the last dose of study drug must be reported. Any occurrence of pregnancy must be recorded on the Pregnancy Report Form Part I and sent via email or fax to the Coordinating Center within 1 business day of learning of the event. See the Safety Data Collection and Reporting section for Coordinating Center contact information.

All pregnancies will be followed for outcome, which is defined as elective termination of the pregnancy, miscarriage, or delivery of the fetus. For pregnancies with an outcome of live birth, the newborn infant will be followed until 30 days old by completing the Pregnancy Report Form Part II. Any congenital anomaly/birth defect noted in the infant must be reported as a serious adverse event.

All reports of pregnancy from sub-sites must be reported to the Vanderbilt Coordinating Center ([contact]) by the site within 24 hours of their knowledge of the event using the Janssen Serious Adverse Event Form. Abnormal pregnancy outcomes (e.g. spontaneous abortion, fetal death, stillbirth, congenital anomaly, ectopic pregnancy) are considered serious adverse events and must be reported using the Serious Adverse Event Form.

Any subject who becomes pregnant during the study must be promptly withdrawn from the study and discontinue further study treatment.

Because the effect of the J&J medicinal product on sperm is unknown, pregnancies in partners of male subjects exposed to a J&J medicinal product will be reported to the Vanderbilt Coordinating Center ([contact]) by the site within 24 hours of their knowledge of the event using the Janssen Serious Adverse Event Form. Depending on local legislation this may require prior consent of the partner.

Follow-up information regarding the outcome of the pregnancy and any postnatal sequelae in the infant will be required.

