9. ELIGIBILITY CRITERIA: INCLUSION

Pre-SCT

1. Adult (≥ 18 y) patients undergoing their first T cell replete allo-HCT for chronic lymphocytic leukemia (CLL), Hodgkin Lymphoma (HL), or the following subtypes of Non-Hodgkin lymphoma: Mantle cell lymphoma (MCL) and follicular center cell lymphoma (FL)
2. Meeting institutional criteria for allo-HCT. Ejection fraction by echocardiogram or MUGA $>40\%$, pulmonary function test with adjusted DLCO $\geq 60\%$
3. Matched (8/8) or mismatched (7/8) related, unrelated HCT
4. Stem cell source: bone marrow, peripheral blood stem cell
5. Disease criteria:

Cohort A:

CLL

- Disease burden: lymph node size <5cm and/or extra-nodal involvement <5 cm

AND

- 17 p deletion (detected by any assay) ($\geq 20\%$ of cells involved if assay is conventional cytogenetics or FISH) or NOTCH mutation at any time point during disease course. Patient should have received at least 1 line of therapy. Prior ibrutinib therapy is permitted.

OR

- Relapsed/refractory CLL ≥ 2 lines of therapy. Prior ibrutinib therapy is permitted

MCL

- Disease burden: lymph node size <5 cm and/or extra-nodal involvement < 5 cm
- Relapsed/refractory MCL ≥ 1 line of therapy. Prior ibrutinib therapy is permitted. Prior autologous HCT is permitted.
- MCL blastoid variant in CR1 or high risk MCL being considered for allo HCT in CR1

Cohort B:

FL

- Disease burden: lymph node size <5cm and/or extra-nodal involvement <5 cm

AND

- Relapsed/refractory FL ≥ 2 lines of therapy. Prior ibrutinib therapy is permitted.

HD

- Disease burden: lymph node size <5cm and/or extra-nodal involvement <5 cm

AND

- Relapsed/refractory HD ≥ 2 lines of therapy

6. Preparative regimen: both reduced intensity and ablative regimens are permitted. Each center will pre-specify the regimen they intend to use during the conduct of the study
7. Donor criteria: HLA $\geq 7/8$ related or unrelated donors.
8. Women of childbearing potential and men who are sexually active must be practicing a highly effective method of birth control during and after the study consistent with local regulations regarding the use of birth control methods for subjects participating in clinical trials. Men must

agree to not donate sperm during and after the study. For females, these restrictions apply for 1 month after the last dose of study drug. For males, these restrictions apply for 3 months after the last dose of study drug.

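### Men must notify partner pregnancies for 3 months after the last dose, but the dated reporting rule for partners stops at 30 days

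*Combined protocol and SAP*

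**What the plan says.** Section 25.7 sets two notification periods. A female subject reports her own pregnancy from consent to 30 days after the last dose. For men the duty runs longer; each is asked to "inform the Investigator if his partner becomes pregnant from the time of consent to 3 months after the last dose of study drug". The longer male period agrees with Section 9, inclusion item 8, on contraception and sperm donation: "For males, these restrictions apply for 3 months after the last dose of study drug".

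The next paragraph of 25.7 states what has to be reported. It covers a pregnancy in a subject or a subject's "partner from the time of consent to 30 days after the last dose of study drug must be reported".

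Two other sections use the same 30-day limit. Section 25.6 lists drug exposure during pregnancy, paternal as well as maternal, as a special reporting situation and adds: "Collection of these events will occur from the time the subject signs consent to 30 days after the last dose of study drug". Section 25.11 repeats that collection window. Section 25.1 also ends at 30 days for special situations including pregnancies, but defers to how the rest of the protocol describes reporting.

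Several sentences in 25.7 have no end date. One is on recording: "Any occurrence of pregnancy must be recorded on the Pregnancy Report Form Part I". Another is on follow-up: "All pregnancies will be followed for outcome". A third is on reports from participating sites: "All reports of pregnancy from sub-sites must be reported to the Vanderbilt Coordinating Center". The closing part of 25.7 also has sites report pregnancies in partners of exposed men within 24 hours of learning of them, again without an end date.

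**The concern.** The protocol treats 3 months as the relevant period for exposure through the father. It sets the male contraception and sperm-donation restrictions at that length, asks men to notify for the same time, and notes in 25.7 that the drug's effect on sperm is unknown. A reporting rule that names partners and stops at 30 days is too short by that standard.

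What is at stake is consistent handling across sites. A partner pregnancy that begins on day 60 after the last dose must be notified to the investigator. A site that follows the 30-day sentence, or the collection windows in 25.6 and 25.11, could regard that notice as outside the reporting window. A site that follows the undated sentences would report it and follow the pregnancy to its outcome. Paternal exposures would then be captured unevenly in a multicentre trial. The primary PFS analysis, the sample size and the stopping rules are not touched.

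**Working it through.** There is no statistical figure to reproduce. The check sets the windows side by side and measures the mismatch.

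| Rule | Where | Ends, counted from last dose |
|---|---|---|
| Male contraception and sperm donation | Section 9, item 8 | 3 months |
| Male subject notifies partner pregnancy | 25.7 | 3 months |
| Female subject notifies own pregnancy | 25.7 | 30 days |
| Pregnancy in subject or partner must be reported | 25.7 | 30 days |
| Special situations, including paternal exposure, collected | 25.6, repeated in 25.11 | 30 days |
| Special situations including pregnancies, as described in the protocol | 25.1 | 30 days |
| Recording, outcome follow-up and sub-site reports of pregnancy | 25.7 | no end date |
| Site reports partner pregnancy within 24 hours of knowledge | 25.7, closing part | no end date |

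1. For female subjects the notification and reporting periods agree at 30 days.
2. For partners of male subjects they do not. The 30-day reporting sentence names the partner, so it cannot be read as meant for female subjects only.
3. Length of the disagreement = 3 months − 30 days. Three calendar months span 89 to 92 days, so the range is 89 − 30 = 59 days to 92 − 30 = 62 days. Taking 3 months as 90 days gives 90 − 30 = 60 days, that is, days 31 to 90.
4. The undated sentences say how, how fast and for how long to report or follow up a pregnancy. They do not say until when a pregnancy qualifies. The only sentence in 25.7 that dates the reporting duty for partners gives 30 days, and a reader can reasonably take it as limiting the undated ones.

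**The case against.** The strongest reply is that partner pregnancies already have their own rule. The closing part of 25.7 is triggered by exposure and the site's knowledge, sets a 24-hour deadline, asks for outcome and infant follow-up, and has no end date. The 3-month notification duty supplies the knowledge. The 30-day sentence says what must be reported up to day 30 and does not tell a site to stop there, so a site can obey every sentence by reporting throughout. This largely stands: it is why the point is an inconsistency and not a gap, and no loss of reports has been shown. It does not remove the conflict, because 25.6 and 25.11 expressly close collection of special situations at 30 days.

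A second reply is that 25.1 keeps collecting adverse events after the window if the principal investigator judges them causally related, and 25.7 treats abnormal pregnancy outcomes as serious adverse events. That narrows the safety consequence, but it does not cover an uneventful pregnancy.

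A third reply concerns the remedy. Correcting 25.7 would largely settle 25.1, which already defers to the rest of the protocol. Conversely, if every general 30-day window needs an exception, the adverse event timeframe in 25.2.2 and the serious adverse event window that opens 25.11 would need one too. Leaving those two alone does not undermine the correction in 25.7, which is the essential edit.

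**Conclusion.** The concern holds. By the protocol's own 3-month standard, the dated reporting window for partners of male subjects is too short, and the text disagrees with itself for about 60 days (59 to 62) after day 30.

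That figure is the width of a wording mismatch. It does not estimate missed reports. It rests on counting 3 months as 89 to 92 days. The documents give no pregnancy rate, and few events are expected in 75 transplant recipients (65 in cohort A plus 10 in cohort B). The consequence is limited to consistent safety capture, so the change is desirable but minor.

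**What to change.** Replace the dated reporting sentence in 25.7 with: *A pregnancy must be reported if it occurs in a female subject between consent and 30 days after her last dose, or in a male subject's partner between consent and 3 months after his last dose.*

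In 25.1, in 25.6 and at the special-situations window in 25.11, add: *except partner pregnancies, which are collected to 3 months after the last dose; see 25.7.* The 30-day window stays for everything else, and the closing rule on partner pregnancies in 25.7 can stay as written.

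The cost is one rewritten sentence and three short exceptions. Men already notify to 3 months, and 25.7 already calls for the site report and outcome follow-up, so no form or visit is added.
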